9.7 Investigator documentation

Prior to beginning the study, the investigator will be asked to comply with ICH E6(R2) 8.2 and Title 21 of the Code of Federal Regulations by providing the following essential documents, including but not limited to:

- IRB/IEC approval
- Original investigator-signed investigator agreement page of the protocol
- FDA Form 1572, fully executed, and all updates on a new fully executed Form FDA 1572
- A curriculum vitae for the investigator and each subinvestigator listed on Form FDA 1572
- Financial disclosure information to allow the sponsor to submit complete and accurate certification or disclosure statements required by applicable regulatory authorities. In addition, the investigators must provide to the sponsor a commitment to promptly update this information if any relevant changes occur during the course of the investigation and for 1 year after the completion of the study.
- IRB/IEC-approved informed consent, samples of site advertisements for recruitment for this study, and any other written information regarding this study that is to be provided to the subject or legal guardian, and
- Laboratory certifications and normal ranges for any local laboratories used by the site.

9.8 Study conduct

The investigator agrees that the study will be conducted according to the principles of ICH E6(R2). The investigator will conduct all aspects of this study in accordance with all national, state, and local laws or regulations. Study information from this protocol will be posted on publicly available clinical trial registers before enrollment of subjects begins.

Fulcrum Therapeutics
Protocol FIS-001-2020

Losmapimod

9.9 Adherence to protocol

The investigator agrees to conduct the study as outlined in this protocol in accordance with ICH E6(R2) and all applicable guidelines and regulations.

9.10 Adverse events and study report requirements

By participating in this study, the investigator agrees to submit reports of SAEs to the sponsor and/or IRB/IEC according to the timeline and method outlined in the protocol. In addition, the investigator agrees to submit annual reports to the study site IRB/IEC as appropriate.

9.11 Investigator's final report

Upon completion of the study, the investigator, where applicable, should inform the institution; the investigator/institution should provide the IRB/IEC with a summary of the study's outcome and the sponsor and regulatory authority(ies) with any reports required.

9.12 Records retention

Essential documents should be retained until at least 2 years after the last approval of a marketing application in an ICH region and until there are no pending or contemplated marketing applications in an ICH region or at least 2 years have elapsed since the formal discontinuation of clinical development of the investigational product. These documents should be retained for a longer period, however, if required by the applicable regulatory requirements or by an agreement with the sponsor. It is the responsibility of the sponsor to inform the investigator/institution as to when these documents no longer need to be retained.

9.13 Publications

After completion of the study, the data will be submitted for reporting at a scientific meeting and for publication in a peer-reviewed scientific journal. In these cases, the sponsor will be responsible for these activities and will work with the investigators to determine how the manuscript is written and edited, the number and order of authors, the publication to which it will be submitted, and other related issues. The sponsor has final approval authority over all such issues.

Data are the property of the sponsor and cannot be published without prior authorization from the sponsor, but data and publication thereof will not be unduly withheld. Further terms concerning publication will be set forth in the clinical trial agreement entered into by the sponsor, the principal investigator, any vendors, and the institution.

Fulcrum Therapeutics
Protocol FIS-001-2020

Losmapimod

10 STUDY MANAGEMENT

The administrative structure will include a DMC (see [Section 8.10](#)).

10.1 Monitoring

The clinical monitor, as a representative of the sponsor, has the obligation to follow the study closely. In doing so, the monitor regularly monitors the trial remotely and will periodically visit the investigator based on local restrictions, in addition to maintaining necessary telephone and letter contact. The monitor will maintain current personal knowledge of the study through observation, review of study records and source documentation remotely, and discussion of the conduct of the study with the investigator and personnel. All relevant source documents will be uploaded into the [REDACTED] Site Source Portal system or access to the electronic medical records will be provided for remote monitoring purposes.

All aspects of the study will be carefully monitored, by the sponsor or its designee, for compliance with applicable government regulation with respect to current GCP and current standard operating procedures.

10.2 Inspection of records

Investigators and institutions involved in the study will permit study-related monitoring, audits, IRB/IEC review, and regulatory inspections by providing direct access to all study records. In the event of an audit, the investigator agrees to allow the sponsor, representatives of the sponsor, or a regulatory agency (eg, FDA or other regulatory agency) access to all study records.

The investigator should promptly notify the sponsor and [REDACTED] of any audits scheduled by any regulatory authorities and promptly forward copies of any audit reports received to the sponsor.

10.3 Management of protocol amendments and deviations

10.3.1 Modification of the protocol

Any changes in this research activity, except those necessary to remove an apparent, immediate hazard to the subject, must be reviewed and approved by the sponsor or its designee. Amendments to the protocol must be submitted in writing to the investigator's IRB/IEC for approval before subjects can be enrolled into an amended protocol.

10.3.2 Protocol deviations

The investigator or designee must document and explain in the subject's source documentation any deviation from the approved protocol. The investigator may implement a deviation from or a change of the protocol to eliminate an immediate hazard to study subjects without prior IRB/IEC approval. As soon as possible after such an occurrence, the implemented deviation or change, the reasons for it, and any proposed protocol amendments should be submitted to the IRB/IEC for review and approval, to the sponsor for agreement, and to the regulatory authorities, if required.

A deviation from the protocol is an unintended or unanticipated departure from the procedures or processes approved by the sponsor and the IRB/IEC and agreed to by the investigator. A significant deviation occurs when there is nonadherence to the protocol by the subject or investigator that results in a significant, additional risk to the subject. Significant deviations can include nonadherence to inclusion or exclusion criteria or nonadherence to FDA regulations or ICH GCP guidelines and will lead to the subject being withdrawn from the study. A list of major protocol deviations will be compiled prior to the start of the study.

Protocol deviations will be documented by the clinical monitor throughout the course of monitoring visits. Principal investigators will be notified in writing by the monitor of deviations. The IRB/IEC should be notified of all protocol deviations in a timely manner.

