Based on the current safety and exposure information, dosing adjustment is likely not needed for subjects with renal insufficiency. However, close monitoring of pharmacokinetics (PK) for such cases will be implemented to ensure that therapeutic concentrations are maintained (refer to **Section 6.2**). For those subjects requiring dialysis, dose adjustment may be needed and will be determined by pre- and post-dialysis PK by the DMC. Adjustments may be recommended by the DMC also for subjects on placebo who develop acute renal failure to prevent unblinding at the sites.

Study treatment discontinuation

Discontinuation of study treatment should be considered if:

- ALT or AST >8 x the upper limit of normal (ULN)
- ALT or AST >5 x ULN for more than 2 weeks
- ALT or AST >3 x ULN and (total bilirubin >2 x ULN or international normalized ratio >1.5) in the absence of reasonable alternative etiology
- ALT or AST >3 x ULN with the appearance of fatigue, nausea, vomiting, right upper quadrant pain or tenderness, fever, rash, and/or eosinophilia (>5%)
- QTcF prolongation with QTcF >500 msec or an increase in QTcF of >60 msec over baseline (confirmed by 2 successive repeat measurements)

In addition, the investigator must permanently discontinue the study drug if continued administration of the study drug is believed to be contrary to the best interests of the subject. The premature discontinuation of study drug might be triggered by an adverse event (AE), a diagnostic or therapeutic procedure, an abnormal assessment (eg, ECG or laboratory abnormalities), pregnancy, or for administrative reasons, in particular noncompliance with the protocol or withdrawal of the subject's consent. The reason for study drug interruption or premature discontinuation must be clearly documented in the eCRF.

Fulcrum Therapeutics
Protocol FIS-001-2020

Losmapimod

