3.4.2 Subject withdrawal

Subjects may withdraw from the study at any time and for any reason without prejudice to their future medical care by the investigator or at the study site. In all cases of impending consent withdrawal, investigators will be given instructions to meet and discuss with the participant their options of continuing in the study. The investigator should ensure understanding and documentation of the reasons for the participant's desire to withdraw consent. Every effort should be made to keep subjects in the study, including if a subject and/or their treating physician decides to prematurely discontinue study treatment. Unless the participant provides their written withdrawal of consent or there is other written documentation by the investigator confirming the participant's verbal intent to completely withdraw from the trial, participants should be followed for all protocol-specified evaluations and assessments. The reasons for subjects not completing the study will be recorded.

A subject may be withdrawn from the study if he or she is lost to follow-up. For subjects to be considered as lost to follow-up, 2 attempts should be made to contact the subject to return for the scheduled study visit. After 2 attempts, a certified letter should be sent to the subject's address requesting the subject to contact the investigator to schedule a follow-up assessment. If no reply is provided by the subject within 30 days of receipt of the certified letter, the subject can then be considered lost to follow-up.

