6.6.1 Early termination visit

When the investigator determines that study treatment will no longer be used, the investigator will perform the ET procedures and document the reason for discontinuation from study treatment in the eCRF. If routine laboratory tests (eg, hematology, serum chemistry) are completed within 7 days before the time of study treatment discontinuation, these tests need not be repeated. Every effort should be made to keep subjects in the study, including if a subject and/or their treating physician decides to prematurely discontinue study treatment.

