8.1.3 Analysis sets

Full Analysis Set (FAS): The FAS will consist of all subjects who are randomly assigned to receive double-blind study drug. All analyses using the FAS will group subjects according to randomized treatment. The primary endpoint, clinical outcomes/status, survival, and pharmacodynamic endpoints will be analyzed using the FAS.

Per Protocol Set (PPS): The PPS will consist of all FAS subjects who fulfill all inclusion/exclusion criteria and do not have any significant protocol deviations. All analyses using the PPS will group subjects according to randomized treatment.

Safety Analysis Set: The safety analysis set is defined as all subjects who are randomized and receive study drug. All analyses using the Safety Analysis Set will group subjects according to treatment actually received. The safety analysis set will be used for all safety and tolerability analyses.

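### Protocol 10.3.2 withdraws subjects from the study after a significant deviation, against the continued follow-up set out in 3.4.2

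*Protocol*

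**What the plan says.** All of the following is current text in protocol v3.0.

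- **10.3.2 Protocol deviations.** A significant deviation is nonadherence, by the subject or the investigator, that "results in a significant, additional risk to the subject". Such deviations can include breaches of the inclusion or exclusion criteria or "nonadherence to FDA regulations or ICH GCP guidelines and will lead to the subject being withdrawn from the study".
- **3.4.2 Subject withdrawal.** "Unless the participant provides their written withdrawal of consent", or the investigator documents a verbal intent to withdraw completely, "participants should be followed for all protocol-specified evaluations and assessments". One other ground is named: "A subject may be withdrawn from the study if he or she is lost to follow-up".
- **6.6.1 Early termination visit.** "Every effort should be made to keep subjects in the study", including after study treatment is stopped early.
- **3.4.1 Dose modifications.** Administrative reasons, "in particular noncompliance with the protocol", appear here as a possible trigger for stopping study drug, not for leaving the study.

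In the SAP, section 3.1.8 treats subjects who leave early for reasons other than death as missing for the key efficacy endpoints and imputes them within arm under missing at random. Section 3.4.1.1 lists the stratification factors, sex, baseline CRP and prior hospital discharge as terms of the imputation model for the primary endpoint; text after that list is redacted. Section 3.3.2 deals with major deviations only through their effect on the analysis populations.

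**The concern.** Sites have two instructions for the same subject. One is to withdraw the subject from the study; the other is to continue every scheduled assessment. Neither section refers to the other.

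If a site applies 10.3.2, Day 28 survival and respiratory status are no longer collected for someone who has not withdrawn consent. Also lost are the Day 7 and Day 14 WHO scale and the oxygen-free days, which are key endpoints in 8.11, and the adverse event reporting that 7.1.1 runs through Day 28. The safety loss falls on subjects whose deviation, by definition, put them at added risk. Withdrawn subjects are not replaced (3.4.3).

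For a dosed subject with no earlier recorded event, an outcome that could have been observed becomes an imputed one. The visible imputation model has no term for deviation or reason for withdrawal, and missing at random is hard to defend for subjects removed because of nonadherence after randomization. The time-to-event sensitivity analyses in SAP 3.4.2 allow for unequal follow-up but cannot recover outcomes that were never collected.

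**Working it through.** **Do the two rules collide?** Take a randomized, dosed subject later found to have breached an entry criterion, with significant added risk, who has not withdrawn consent and can be reached. Under 10.3.2 the subject leaves the study. Under 3.4.2 neither named ground for leaving applies, so assessments should continue to Day 28. Both cannot be followed.

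**Does any text settle it?** The 10.3.2 sentence is the same in v1.0, v2.0, v2.1 and v3.0. In v1.0 it agreed with 3.4.2, which then listed noncompliance among the reasons for study withdrawal. From v2.0 that reason is gone from 3.4.2. The v2.0 entry in the Summary of Changes gives the intent, after FDA feedback, that subjects leave the study only for withdrawn consent or loss to follow-up. That entry does not mention 10.3.2. The two clarification memos, the administrative letter and SAP section 6 do not address the point.

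**The plan's own power.** Inputs: event rates 0.18 and 0.30 (protocol 8.6), 103 then 205 per arm, futility bound −0.67873 and final bound −1.91358 (Table 6).

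- Unpooled variance: 0.18 × 0.82 + 0.30 × 0.70 = 0.3576.
- Drift at the interim: 0.12 / √(0.3576/103) = 2.037. Drift at the final analysis: 0.12 / √(0.3576/205) = 2.873. Correlation: √(103/205) = 0.709.
- P(Z1 < −0.67873 and Z2 < −1.91358), bivariate normal: power 0.802 and one-sided type I error 0.0250. The probability of stopping under the null is 0.751 (stated 0.75135), and under the alternative 0.087 (stated 0.08871).

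The stated power of approximately 80% is reproduced.

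**Illustrative loss.** Assume that an equal share w of each arm is withdrawn, unrelated to outcome, and that imputation recovers nothing. Then n becomes n(1 − w) and both drifts shrink by √(1 − w).

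| w | n per arm | Final drift | Power | Type I error |
|---|---|---|---|---|
| 0 | 205 | 2.873 | 0.802 | 0.025 |
| 0.02 | 200.9 | 2.844 | 0.794 | 0.025 |
| 0.05 | 194.75 | 2.800 | 0.782 | 0.025 |

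If the event risk among the withdrawn is k times the arm rate in both arms, the retained rate is p(1 − wk)/(1 − w), and the difference becomes −0.12(1 − wk)/(1 − w). At w = 0.05 this is −0.123 for k = 0.5 and −0.114 for k = 2, with power 0.796 and 0.753. When the two arms have equal rates, the same formula gives a difference of zero. Bias under the null therefore needs loss that is both related to outcome and different between the arms.

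**The case against.** **The intent is on record.** The v2.0 change-log entry makes it fairly clear that 3.4.2 is meant to govern, so this looks like a sentence left unedited, not a live choice between two rules. That stands as an account of how the conflict arose. But a change log does not amend 10.3.2, and sites read 10.3.2 as an instruction.

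**The wording is softer than it may seem.** Section 3.4.2 says 'should', and 10.3.2 reaches only deviations with significant added risk. A reader might infer that full follow-up is strictly mandatory, or that every eligibility error triggers withdrawal; the text supports neither. For deviations that do meet the threshold, the conflict remains.

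**The Per Protocol Set.** Protocol 8.1.3 limits that set to subjects who "do not have any significant protocol deviations", from which a reader might infer that the protocol has already chosen to keep such subjects in the study. It has not: leaving them out of that set is compatible with either rule, and the SAP's analysis populations do not include such a set.

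**Type I error.** A reader might infer that the conflict inflates it. That takes an extreme construction. Suppose 5% are lost in the losmapimod arm and none on placebo, with an event risk of 60% among the lost against 30% overall and nothing recorded before withdrawal. The retained rate is then 0.30 × 0.90/0.95 = 0.284, and the one-sided error is 0.053. If half of those events had been recorded first, the rate is 0.285/0.965 = 0.295 and the error 0.032. Nothing documents such an imbalance. Eligibility breaches are fixed before randomization, sites and sponsor are blinded (5.4.2), and about 10 withdrawals falling independently of arm would all be on losmapimod with probability 0.5¹⁰, about 1 in 1,000.

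**Conclusion.** Section 10.3.2 is wrong as written: its withdrawal clause contradicts 3.4.2 and 6.6.1 in the current protocol, and no operative passage resolves it. Severity is low to moderate. The loss is of outcome and safety data that could have been observed, for subjects who have not withdrawn consent.

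The size is unknown because the documents give no deviation rate. The 2% and 5% losses are assumptions, not bounds, and they take imputation to recover nothing. On that basis the cost is about one to two points of power with type I error unchanged. Outcome-related loss that is equal in both arms would also move the estimated difference slightly. The documents do not support a claim of inflated type I error.

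**What to change.** Replace the withdrawal clause in 10.3.2 with a cross-reference, for example: *A significant deviation does not by itself end study participation. Unless consent is withdrawn or the subject is lost to follow-up, every scheduled evaluation continues under Section 3.4.2.* The wording should cover all scheduled assessments. Naming only Day 28 survival and respiratory status would create a third rule and drop adverse events, the Day 7 and Day 14 WHO scale and oxygen-free days.

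Whether such a deviation also affects study drug has to be reconciled by the sponsor between 10.3.2 and 3.4.1; nothing is proposed on that here.

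The cost is a one-sentence change in a protocol amendment with IRB/IEC approval (10.3.1). It adds no assessments beyond those already in 3.4.2 and Table 1.

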10.4 Study termination

Although Fulcrum Therapeutics has every intention of completing the study, Fulcrum reserves the right to discontinue the study at any time for clinical or administrative reasons. Should termination of

Fulcrum Therapeutics
Protocol FIS-001-2020

Losmapimod

the study be required, the sponsor will promptly inform the investigator and the IRB/IEC and provide them with a detailed written explanation. Fulcrum and the investigator will assure that adequate consideration is given to the protection of the subjects' interests. The sponsor has no plans to provide study drug to subjects after study closure or termination. The obligations to provide study results for subjects and reports to IRB/IEC shall continue as required by applicable laws and regulations.

At any time, the sponsor, the investigators, or the IRBs/IECs may terminate this study for reasonable cause. Conditions that may lead to reasonable cause and warrant termination include, but are not limited to the following:

- Subject or investigator noncompliance
- Unsatisfactory subject enrollment
- Lack of adherence to protocol procedures
- Lack of evaluable and/or complete data
- Potentially unacceptable risk to study subjects
- Decision to modify drug development plan
- Decision by the regulatory authority

Written notification that includes the reason for the clinical study termination is required.

The end of the study is defined as the date on which the last subject completes the last visit (includes the safety follow-up visit).

10.5 Final report

Whether the study is completed or prematurely terminated, the sponsor will ensure that the clinical study reports are prepared and provided to the regulatory agency(ies) as required by the applicable regulatory requirement(s). The sponsor will also ensure that the clinical study reports in marketing applications meet the standards of the ICH harmonised tripartite guideline E3: Structure and content of clinical study reports.

Where required by applicable regulatory requirements, an investigator signatory will be identified for the approval of the clinical study reports. The investigator will be provided reasonable access to statistical tables, figures, and relevant reports and will have the opportunity to review the complete study results.

Upon completion of the clinical study reports, the sponsor will provide the investigator with the full summary of the study results. The investigator is encouraged to share the summary results with the study subjects, as appropriate. The study results will be posted on publicly available clinical trial registers.

Date: 18-September-2020

This Protocol Clarification memo is to further clarify some items of the protocol FIS 001-2020 LOSVID.

1. Primary Endpoint:

Please note that the primary endpoint for FIS 001-2020 was defined in agreement with the United States FDA, with a focus on reducing a bad outcome. Fulcrum will ensure that the benefit to participants will be made clear in case of positive results.

2. Vaccinations:

Vaccinations are not to be administered to participants during the study.

3. Exclusion Criterion 8

Significant history or evidence of clinically significant disorder, condition, current illness, illicit drug or other addiction, or disease that, in the opinion of the Investigator, would pose a risk to subject safety or interfere with the study evaluation, procedures, or completion.

Clarification: Special attention should be paid to patients with diagnosis of current active tuberculosis (TB) or, if known, latent TB treated for less than 4 weeks with appropriate anti-tuberculosis therapy according to local guidelines. Those patients should be excluded from the study.

4. Visit and Assessment Schedule: Electrocardiogram

ECGs should be conducted for eligibility, after 7 days of treatment and at other times of the study, if clinically indicated.

2020-Sep-18

Clinical Operations Lead, Fulcrum Therapeutics

CLINICAL STUDY PROTOCOL

A Phase 3, Randomized, Double-Blind, Placebo-Controlled Study of the Safety and Efficacy of Losmapimod in Adult Subjects with COVID-19 (LOSVID STUDY)

Short Title: Losmapimod safety and efficacy in COVID-19 (LOSVID Study)

Version: 2.1

Date: 10-Jul-2020

Study number: FIS-001-2020

Sponsor:
Fulcrum Therapeutics
[name]
[name]
USA

Sponsor signatory: [Redacted] MD

Information described herein is confidential and may be disclosed only with the express
written permission of the sponsor.

Fulcrum Therapeutics
Protocol FIS-001-2020

Losmapimod

CONTACT DETAILS

SPONSOR

Fulcrum Therapeutics
[name]
[name]
USA

Clinical Trial Leader

[REDACTED] MD

Telephone: [REDACTED]

e-mail: [REDACTED]

Drug Safety Physician

[REDACTED] MD

Telephone: [REDACTED]

e-mail: [REDACTED]

Fulcrum Therapeutics
Protocol FIS-001-2020

Losmapimod

SIGNATURE PAGE - INVESTIGATOR

Study Title

A Phase 3, Randomized, Double-Blind, Placebo-Controlled Study of the Safety and Efficacy of Losmapimod in Adult Subjects with COVID-19 (LOSVID STUDY)

